## **8.2.3 Matching**

Not applicable

## **8.2.4 Baseline Period**

The baseline period will be identified as 365 days before the index date (exclusion the index date). For three cohorts of patients with study medication (romosozumab, PTH analogs (teriparatide, abaloparatide) or oral alendronate), we will use all historical data prior to index date (exclusive) to identify new use of the index drug.

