Three cohorts will be created mutually and defined based on the prescriptions received for:

- Romosozumab
- PTH analogs: teriparatide, abaloparatide
- Oral alendronate

- Covariates

- Patient and healthcare characteristic
- Fracture risk factors
- Cardiovascular risk factors
- Use of cardioprotective therapies
- Historical use of anti-osteoporosis drugs
- Level of renal insufficiency

- Study Sample Size

Using the MID-NET 2021 open data, we estimated the number of patients who received romosozumab, teriparatide, or oral alendronate over 5.5 years. The expected sample size for this study is: 3,850 patients for romosozumab, 8,500 patients for teriparatide, and 60,000 patients for oral alendronate.

- Data Analysis

- Summary Statistics:

Patient demographic and clinical characteristics will be summarized by cohort of exposure. Discrete variables will be summarized using frequencies and proportions, and continuous variables will be summarized using means and standard deviation (SD) or median and interquartile range (IQR). Incidence rate (number of events divided by person-time of follow-up) of the various outcomes in each exposure cohort will be estimated along with 95% confidence intervals (CI) as a measure of precision.

- Approach to primary objective:

Propensity scores will be calculated for each patient using multiple logistic regression modelling based on baseline demographic characteristics and clinical characteristics. Inverse probability of treatment weights (IPTW) will be created using propensity scores to minimize the measured confounding in the comparison of patients initiating romosozumab relative to patients initiating other specific osteoporosis therapies. Standardized mean differences (SMD) will be used to assess the differences in baseline patient characteristics between the treatment groups. Negative control outcome analyses will be used to detect presence of unmeasured confounding. COX proportional hazards model in the weighted sample will be used to estimate hazard ratio.

- Approach to secondary objective:

The same approach will be performed by the level of renal insufficiency:

1) no chronic renal disease (or eGFR  $\geq 90$  mL/min/1.73 m^2), 2) stage I or II Chronic Kidney Disease (CKD) (or eGFR 60-89 mL/min/1.73 m^2), 3) stage III CKD (or eGFR 30-59 mL/min/1.73 m^2), or 4) stage IV or V (or eGFR  $< 30$  mL/min/1.73 m^2).

- Bias analysis:

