## **8.2.2 Subject Eligibility**

### **8.2.2.1 Inclusion Criteria**

Three cohorts of patients defined by new initiation of romosozumab, PTH analogs (teriparatide, abaloparatide) or oral alendronate from 4 March 2019 onwards to one year prior to the end of available data.

Patients at least 50 years of age at date of new treatment initiation.

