### **8.2.2.2 Exclusion Criteria**

Patients without at least 365 days before new treatment initiation.

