### **8.3.3 Covariate Assessment**

Covariates that might influence osteoporosis treatment choice (ie, measures of prognosis) and are risk factors for various adverse events that could be assessed in safety evaluation are included to control for confounding. Sex, age and year of index date will be included as a covariate. All available historical data will be used to assess

history of fracture, history of pharmacologic therapy for osteoporosis, history for cardiovascular risk factor, history of cardioprotective therapies and or osteoporosis-related medication. Each covariate will be identified using a case ascertainment algorithm that incorporates individual or combinations of inpatient and outpatient ICD-10 diagnosis codes, drug codes, procedure codes, laboratory test codes, and date information from the MID-NET system. Covariates with a prevalence of 0.5% or less in the feasibility assessment within MID-NET will not be included in this study.

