**Table 3. List of covariates**

Characteristic	MID-NET	Note/ Covariate assessment period
Age, mean (SD)	Yes	On index date
Race/ethnicity	No	Most of all is Japanese
Sex (Male, female)	Yes	On index date
Year of cohort entry	Yes	On index date
Lifestyle risk factors		The closest measurement taken within one year before the index date, including the index date itself.
Smoking index	Yes	This information might be only recorded when patients are admitted to the hospital.
Information of lab value		The closest measurement taken within one year before the index date, including the index date itself.
Height, cm, mean (SD)	Yes	
Weight, kg, mean (SD)	Yes	
Body mass index, mean (SD)	Yes	Calculated with height and weight, kg/m 
Serum creatinine, mg/dL, mean (SD)	Yes	
eGFR, mL/min/1.73 m 	Yes	% among three cohorts to be confirmed
Level of renal insufficiency a		Calculated with serum creatine level. Classified into four groups. >= 90 (Normal); 60 -< 90 (Mild); 30 -< 60 (Moderate); < 30 (Severe)
Fasting plasma glucose, mg/dL, Mean (SD)	Yes	
HbA1c, %, Mean (SD)	Yes	
HDL-C, mg/dL, Mean (SD)	Yes	
LDL-C, mg/dL, Mean (SD)	Yes	
Triglyceride level, mg/dL, Mean (SD)	Yes	
History of healthcare utilization		Within one year prior to index
Number of inpatient hospitalizations	Yes	
Number of outpatient visits	Yes	
Number of cardiovascular-related hospital days	Yes	
Number of serum creatinine tests	Yes	% among three cohorts to be confirmed
Number of lipid-related lab tests	Yes	% among three cohorts to be confirmed
History of fracture	Yes	All available history unless otherwise specified
Any fracture	Yes	
Vertebral fractures	Yes	
Hip fracture	Yes	

Characteristic	MID-NET	Note/ Covariate assessment period
History of fracture hospitalizations	Yes	
Osteoporosis diagnosis	Yes	
History of use of anti-osteoporosis drugs		All available history unless otherwise specified
Oral bisphosphonates	Yes	
IV bisphosphonates	Yes	
Anti-RANKL antibody (Denosumab)	Yes	
PTH analogs (Teriparatide or abaloparatide)	Yes	
Selective estrogen receptor modulators (Raloxifene, bazedoxifene)	Yes	
Estrogen replacement therapy	Yes	
Historical use of the medication that increased fracture or osteoporosis risk	Yes	Fracture/OP risk factors, Within one year prior to index
Anticonvulsant		
Antidepressant	Yes	
Antiparkinsonian	Yes	
Antipsychotic	Yes	
Benzodiazepine	Yes	
NSAIDs and COX-2 inhibitor	Yes	

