## **8.7.2 Planned Method of Analysis**

### **8.7.2.1 General Considerations**

Given that MID-NET database is not accessible for now, descriptive analysis will be conducted prior to propensity score weighting portion of this study. To describe the incidence rate for outcomes, by romosozumab therapy, by PTH analogs, and by oral alendronate, the number of patients with events will be divided by person-time of follow-up. Incidence rate as well as hazard ratio will be accompanied by the corresponding 95% confidence intervals (CI) as a measure of precision.

We assume that measured and unmeasured confounding exist, and plan to perform a set of analyses to assess the comparability between treatment groups. Standardized mean differences (SMD) will be used to assess how different the baseline characteristics are between the treatment groups before and after propensity score weights are applied. We will consider the measured confounders with SMD values less than 0.1 as having negligible differences (Austin, 2009). In addition, negative control outcome analyses will be performed to rule out any potential unmeasured confounders (McGrath et al., 2020). For each negative control outcomes, risk difference and risk ratio in negative control outcomes will be calculated. The comparability of treatment groups will be explored by examining overall trends in effect estimates and the precision of CI across all negative control outcomes within an exposure contrast. We will assume there is significant uncontrolled confounding if the measure of association is not likely to be null.

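### New use is tested only for each patient's own index drug, so former romosozumab users can enter the comparator cohorts, and prior PTH-analog use, read at class level, cannot be balanced

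*Protocol*

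**What the plan says.** Section 8.2.2.1 admits "Three cohorts of patients defined by new initiation of romosozumab, PTH analogs (teriparatide, abaloparatide) or oral alendronate from 4 March 2019 onwards". The only exclusion, in section 8.2.2.2, is "Patients without at least 365 days before new treatment initiation". Section 8.2.4 then defines newness: "we will use all historical data prior to index date (exclusive) to identify new use of the index drug". None of these sections mentions earlier use of the other two study drugs.

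Section 8.3.3 names "history of pharmacologic therapy for osteoporosis" as a covariate assessed over all available history. Under osteoporosis-drug history, Table 3 lists "Oral bisphosphonates" and PTH analogs; romosozumab is absent from that list.

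The Abstract says "Three cohorts will be created mutually and defined based on the prescriptions received for" the three treatments, with no washout or re-entry rule. Section 8.2.5 makes a switch a censoring event but does not say whether the switcher may enter a second cohort. Table 1 gives a 12-month romosozumab course.

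Sections 8.7.1.2 and 8.7.2.4 plan pairwise propensity scores with inverse probability of treatment weighting (IPTW) to the overall population. Section 8.7.2.1 sets the balance standard: "We will consider the measured confounders with SMD values less than 0.1 as having negligible differences".

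**The concern.** The new-use rule is asymmetric within each pair. A PTH initiator must have no PTH use in all recorded history, whereas a romosozumab initiator may have any amount. If PTH is judged as a class, romosozumab patients with prior PTH use have no possible counterpart in the PTH arm. The weighted hazard ratio then includes patients for whom the data hold no comparison, and a listed covariate fails the balance standard for reasons that no propensity model can mend.

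In the other direction, a patient who finishes or stops romosozumab and then starts alendronate or a PTH analog meets every stated criterion for the comparator cohort. The study asks whether romosozumab raises cardiovascular risk, yet exposed people can be counted in the reference group without adjustment. If risk persists after stopping, this pulls the hazard ratio towards 1. If those who move on are mainly event-free survivors of the first course, it could push the other way.

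**Working it through.** **Inputs.** From section 8.5: 3,850 romosozumab, 8,500 PTH and 60,000 alendronate patients; rates of 0.004 or 0.01 per person-year; 0.6 or 0.8 years of follow-up. From section 8.7.2.1: the 0.1 limit. Shares of prior use, crossover shares, rate ratios and the true hazard ratio (HR) of 2.0 are assumptions, because the protocol gives none.

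**The plan's own figures.** 700 × 5.5 = 3,850, as stated. 1,551 × 5.5 = 8,530.5, stated as 8,500. Table 4 follows closely from exp(±1.96 × √(1/d₁ + 1/d₂)), where d = patients × rate × years. For PTH at 0.004 and 0.6 years, d₁ = 9.24 and d₂ = 20.4, giving (0.46, 2.18) against the stated (0.45, 2.18).

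**Balance, romosozumab versus PTH as a class.** Let x be the share of romosozumab patients with prior PTH use.
- Their propensity score tends to 1, so each keeps a weight of about 1. The weighted romosozumab arm totals 3,850 + 8,500 = 12,350.
- Weighted prevalence is p = 3,850x / 12,350 in the romosozumab arm and 0 in the PTH arm.
- SMD = p / √(p(1−p)/2) = √(2p/(1−p)).
- SMD = 0.1 gives p = 0.01/2.01 = 0.498%, or about 61 patients; 61/3,850 = 1.6%.
- x = 10%: p = 385/12,350 = 3.12%, SMD = 0.25 (0.47 before weighting).
- x = 20%: p = 770/12,350 = 6.23%, SMD = 0.36 (0.71 before weighting).

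**Effect of that imbalance on a true HR of 1.** If prior PTH use carries rate ratio r, the weighted HR becomes 1 + p(r−1). For r from 1.25 to 2.0 this is 1.01 to 1.03 at x = 10% and 1.02 to 1.06 at x = 20%.

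**The planned sensitivity analysis.** The standard mortality ratio weighting (SMRW) in section 8.7.2.5.4 makes romosozumab resemble the comparator, with weight (1−PS)/PS for romosozumab patients. As the score tends to 1 this tends to 0. SMRW therefore removes the patients that IPTW keeps, and the two analyses differ in population for this reason alone.

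**Former romosozumab users among comparators.** If a fraction f of comparator person-time carries the full romosozumab risk, observed HR = HR / (1 + f(HR−1)). With a true HR of 2.0, and taking shares of patients as shares of person-time:

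| Comparator | Romosozumab patients crossing over | f | Observed HR |
|---|---|---|---|
| Alendronate | all 3,850 (ceiling) | 3,850/60,000 = 6.4% | 1.88 |
| Alendronate | 20% (770) | 1.3% | 1.97 |
| PTH | 20% (770) | 770/8,500 = 9.1% | 1.83 |
| PTH | 44% (1,700) | 20% | 1.67 |

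**The case against.** **Class or molecule.** The empty cell depends on reading the index drug as the PTH class. Section 8.3.1 describes teriparatide and abaloparatide exposure separately, and section 8.3.2 names only teriparatide among the index medications. At molecule level, a former teriparatide user could enter as a new abaloparatide user and the cell would not be empty. This stands, and it means the protocol must say which reading applies.

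**Alendronate.** A reader might infer that the propensity score also separates in the alendronate contrast. It need not. The listed covariate is the whole class of oral bisphosphonates, and users of other members of that class can enter the alendronate arm. Prior alendronate is still zero by design in that arm, but the imbalance is hidden inside the class variable.

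**Size of dilution.** A reader might also fear that a fifth of comparator follow-up comes from former romosozumab users. For alendronate the counts rule this out on an unweighted basis. For PTH it would require 44% of romosozumab patients to go on to a PTH analog, which nothing in the protocol supports. Full carry-over of risk is also unsupported; the study's own risk window closes at discontinuation.

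**Overlap.** The Abstract wording probably means mutually exclusive cohorts, which would discourage counting one person twice. Even so, it sets no washout on the other drug and does not say which episode counts.

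**Left to the SAP.** Section 8.9.3 defers model building, and dropping a covariate is a modelling decision. But eligibility and the new-use test are fixed in the protocol, and leaving the covariate out would hide the imbalance without removing it.

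**Consequence.** Exceeding 0.1 triggers no stated action, and the illustrative shifts in the hazard ratio are small beside intervals as wide as 0.45 to 2.18. This stands, and it limits the seriousness of the point.

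**Conclusion.** The concern holds in limited form and should be fixed. As written, the rules allow former romosozumab users into both comparator cohorts with no adjustment. With PTH judged as a class, they also make prior PTH use impossible to balance in that contrast. The balance failure needs only about 1.6% prior PTH use in the romosozumab arm; whether that share is reached is not known from the protocol.

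The resulting bias in the hazard ratio is unknown and probably modest. In the alendronate contrast, a true hazard ratio of 2.0 would fall no lower than about 1.88, unweighted and with full carry-over of risk. Dilution can be larger only in the PTH arm. Entry of former romosozumab users is permitted by the text, not stated by it. The protocol does not support the inference that either primary comparison is invalid.

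**What to change.** Amend sections 8.2.2 and 8.2.4, and Table 3 where needed, as follows:

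1. Exclude anyone with prior romosozumab use from both comparator cohorts.
2. In each pairwise contrast, require no prior use, over all history, of either drug in the pair, and take the first qualifying initiation per patient.
3. State that new use of PTH analogs is judged at class level, and replace the Abstract wording with an explicit exclusivity and re-entry rule.
4. Drop the history item that becomes constant from that contrast's propensity model. Prior PTH use stays useful against alendronate, and prior oral bisphosphonate use against PTH.
5. Recount the expected cohorts, since section 8.5 counts users and not drug-naive initiators.

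The cost is fewer romosozumab patients and a narrower population. At a rate of 0.004 and 0.6 years, an assumed 20% loss (3,080 left, 7.4 events) widens the PTH interval to (0.43, 2.32). The alendronate interval goes from a recomputed (0.51, 1.94) to (0.48, 2.09). An assumed 50% loss gives (0.36, 2.75) and (0.40, 2.53). Also removing 5 to 10% of comparators moves the upper limits by about 0.03 at most. The unrestricted cohort can be kept as a sensitivity analysis.

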## **8.2.5 Study Follow-up**

Patients will be followed from the initiation of romosozumab, PTH analogs or oral alendronate (index date) through the first occurrence of any of following: endpoint, discontinuation of the study medication (including medication switch), one year after index date, end of available data in the database, or death.

## **8.3 Variables**

### **8.3.1 Exposure Assessment**

1. Romosozumab: the dosing interval for romosozumab 210mg (Evenity®) is once every 30 days. Patients will be considered continuously exposed to Evenity until a gap beyond the dosing interval is observed. The censoring date for treatment discontinuation will be the last administration date plus an appropriate window defined in statistical analysis plan (SAP).
2. PTH analogs: the dosing intervals for teriparatide vary by dosage form. Patients will be considered continuously exposed to teriparatide until a gap beyond the dosing interval is observed. In addition, abaloparatide is once daily from a self-injector. Patients will be considered continuously exposed to abaloparatide until a gap beyond the dosing interval is observed. The censoring date for treatment

discontinuation will be the last administration date plus an appropriate window defined in SAP.

3. Oral alendronate: The dosing intervals for alendronate vary by prescription. Days' supply associated with the prescription will be used to determine the dosing interval. Patients will be considered continuously exposed from the date of first prescription until a gap beyond the completion of the last day's supply and next prescription is observed. The censoring date for treatment discontinuation of oral bisphosphonates will be the last dispensing date plus an appropriate window defined in SAP.

### 8.3.2 Outcome Assessment

Outcome of primary objective and secondary objective:

Cardiovascular end points will be defined using algorithms that have been previously validated in Japan administrative claims databases and recommended by agency (Ando et al, 2018; Nakai et al, 2021; PMDA, 2023a; PMDA, 2023b; PMDA, 2023c).

Endpoint will be the first admission date for each outcome, and the event will be identified with a diagnosis related to primary, admission-causing or most-resourcing categories.

We will use the admission date as the event date to capture the earliest sign of the event. We recognize that the admission date may not represent the actual onset of event if it occurs during hospitalization. However, we expect that this effect is likely small in general, since the average hospital stay related to cardiovascular events was reported to be approximately 15 days (JCS, 2023). Moreover, the subgroup of the patients using index medication (ie, romosozumab, teriparatide, or oral alendronate) during hospitalization is less than 10% (MHLW, 2023a). Therefore, the use of admission date as the date of event occurrence is appropriate for this study.

CCI

**Table 2. Algorithms of outcome definitions**

Outcome	Definition
CCI	

CCI

### **8.3.3 Covariate Assessment**

Covariates that might influence osteoporosis treatment choice (ie, measures of prognosis) and are risk factors for various adverse events that could be assessed in safety evaluation are included to control for confounding. Sex, age and year of index date will be included as a covariate. All available historical data will be used to assess

history of fracture, history of pharmacologic therapy for osteoporosis, history for cardiovascular risk factor, history of cardioprotective therapies and or osteoporosis-related medication. Each covariate will be identified using a case ascertainment algorithm that incorporates individual or combinations of inpatient and outpatient ICD-10 diagnosis codes, drug codes, procedure codes, laboratory test codes, and date information from the MID-NET system. Covariates with a prevalence of 0.5% or less in the feasibility assessment within MID-NET will not be included in this study.

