Corticosteroids (oral or injectable)	Yes	
Opioids	Yes	
Proton-pump inhibitor	Yes	
History of other comorbidities that increased fracture or osteoporosis risk		Fracture/OP risk factors. Within one year prior to index
Rheumatoid arthritis	Yes	
Systemic Lupus Erythematosus	Yes	
Chronic obstructive pulmonary disease	Yes	
Asthma	Yes	
Pneumonia	Yes	
Parkinsonism	Yes	
Dementia	Yes	
Depression	Yes	
Schizophrenia	Yes	
Sepsis or septicemia	Yes	
Sleep apnea	Yes	
Vitamin D deficiency	Yes	
History of cardiovascular events		All available history unless otherwise specified
Myocardial infarction within 1 year prior to index	Yes	Within one year prior to index
Myocardial infarction $\geq$ 1 year prior to index	Yes	$\geq$ 1 year prior to index
CCI within 1 year prior to index	Yes	Within one year prior to index
CCI $\geq$ 1 year prior to index	Yes	$\geq$ 1 year prior to index
History of CV risk factors		Within one year prior to index
Atherothrombosis	Yes	
Heart failure	Yes	
Peripheral artery disease	Yes	

Characteristic	MID-NET	Note/ Covariate assessment period
Cerebrovascular disease	Yes	
Coronary artery disease	Yes	
Angina (including stable and unstable)	Yes	
Atrial fibrillation	Yes	
Conduction disorder	Yes	
Hypertension	Yes	
Hyperlipidemia	Yes	
Hypercholesterolemia	Yes	
Obesity	Yes	
Peripheral vascular disease	Yes	
Transient ischemic attack	Yes	
Type 2 diabetes mellitus	Yes	
CKD	Yes	
Chronic kidney disease (stage III, IV and V) without dialysis	Yes	
Chronic kidney disease (stage III, IV and V) with dialysis	Yes	
End stage renal disease	Yes	
History of cardioprotective therapies		Within one year prior to index
Diuretic		Antihypertensive
Beta-blocker		Antihypertensive
Calcium Channel blockers		Antihypertensive
Angiotensin Converting Emzyme (ACEI)/ Angiotensin Receptor Blockers (ARBs)	Yes	Antihypertensive
Insulin	Yes	Anti-diabetes
Metformin	Yes	Anti-diabetes
GLP-1 receptor agonists	Yes	Anti-diabetes
Thiazolidinediones	Yes	Anti-diabetes
Sulfonylureas	Yes	Anti-diabetes
SGLT- 2 inhibitors	Yes	Anti-diabetes
DPP- 4 inhibitors	Yes	Anti-diabetes
Statins (any kind)	Yes	lipid lower agents
Ezetimide	Yes	lipid lower agents
Statins + ezetimide combinations	Yes	lipid lower agents
PCSK9i	Yes	lipid lower agents
Other lipid lowering drugs (fibrates, gemfibrozil, Niacin, Cholestyramine)	Yes	lipid lower agents
Aspirin	Yes	Antiplatelets/ antithrombotic
Clopidogrel and other antiplatelet	Yes	Antiplatelets/ antithrombotic

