### 8.7.2.4 Analysis of the Primary, Secondary, and CCI

Primary endpoint is consistent with primary objective.

- Composite endpoint of hospitalized AMI, cerebral hemorrhage and cerebral infarction

Secondary endpoint is consistent with secondary objective.

- Composite endpoint of hospitalized AMI, cerebral hemorrhage and cerebral infarction

CCI

We will use two methods to estimate the incidence of each endpoint. First, we will calculate simple incidence rates (total number of patients with at least one event in the cohort divided by the sum of person-time to the first censoring event in the cohort) multiplied by 100 for each outcome and cohort. These rates do not account for treatment selection. Second, we will estimate propensity scores for each patient in the cohort using multivariable logistic regression with baseline covariates related to patient and clinical characteristics (see Section 8.3.3). The propensity score balances the distribution of observed covariates between treatment groups. We will include covariates that are either true confounders (to reduce bias) or related to the outcome (to increase precision). We will avoid covariates that are only related to the exposure but weakly related to the outcome, as they may decrease precision without reducing bias much (Brookhart et al, 2006). We will use inverse probability of treatment weights (IPTW) to estimate the rates of each outcome by time t in the overall patient population.

Specifically,  $F(T(a) < t)$  will be estimated with:

$$F(T(a) < t) = \frac{1}{n} \sum_{i=1}^n \frac{I(T_i < t) I(A_i = a) \Delta_i}{\Pr(\Delta_i = 1 | A_i, W_i)}$$

where  $A_i$  is an indicator of the observed treatment assignment,  $T(a)$  is the time of the (possibly counterfactual) outcome that would be observed if the patient were treated with  $A_i=a$ , and  $\Delta_i$  is an indicator that the patient was uncensored.

The propensity score model,  $\Pr(A_i=a|W_i)$ , will be estimated using logistic regression, and will contain a rich set of baseline covariates detailed in Section 8.3.3. We will estimate the hazard ratio and 95% confidence interval bands at 12 months by using COX proportional hazards model. Patients will be censored if any of the following happen: they discontinue the study medication (or switch to a different medication), one year from the start of study medication (index date), end of available data in the database, or death, whichever is earliest.

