##### **8.9.1.1 Measurement Error(s)/Misclassification(s)**

MID-NET is an open healthcare system that may result not capture all the relevant data on exposure, outcome and covariates for the study. Since romosozumab appears to have more complete data related to other specific therapies in the MID-NET system, we will evaluate it with an external database that is a closed healthcare system. This will help us assess if there is any differential bias between the treatment groups. Moreover, the information on social behavior such as smoking because the history of smoking is only available in inpatient claims. Since alcohol consumption and risk of fall could not be directly measured from the diagnoses, these variables were not included in this study.

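### Fracture, osteoporosis-drug and remote cardiovascular history are read over look-backs of unequal length, and look-back length is not in the propensity model, so balance on recorded history need not mean balance on true history

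*Protocol*

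**What the plan says.** - **Eligibility.** Section 8.2.2.2 excludes "Patients without at least 365 days before new treatment initiation". It sets a minimum length of record and no maximum.
- **Look-back.** Section 8.3.3 says "All available historical data will be used to assess" a list of histories. In Table 3 the blocks for fracture, anti-osteoporosis drugs and cardiovascular events carry the note "All available history unless otherwise specified".
- **Cardiovascular events.** Table 3 splits MI into two rows, "Myocardial infarction within 1 year prior to index" and "Myocardial infarction $\geq$ 1 year prior to index". A second event, redacted in the public text, is split in the same way. The recent row has the same window for everyone; the remote row has no outer limit.
- **Propensity model.** Section 8.7.2.4 says it "will contain a rich set of baseline covariates detailed in Section 8.3.3". Table 3 has no row for length of record. The nearest items are calendar year ("Sex, age and year of index date will be included as a covariate") and utilization counts taken over one year.
- **Balance.** Section 8.7.2.1 treats an SMD below 0.1 on a measured confounder as negligible.
- **Data span.** Section 8.2.1 has data reaching back 365 days before index. Section 8.2.4 uses everything before index to establish new use, and Section 8.3.3 uses everything for the histories.
- **Windows.** The text of Section 8.3.3 gives cardiovascular risk factors and cardioprotective therapies an open window. Table 3 gives them one year.

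**The concern.** A patient with exactly 365 days of record has essentially no observable time in which a remote MI could appear, and is coded as having none. A patient with the same history and several more years in the network can be coded as having one. Absence of data becomes absence of disease, and Section 8.7.2.2 rules out imputation. Year of index does not repair this: a long-standing patient and one first seen 365 days earlier can start treatment in the same year.

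Inverse probability weighting equalizes what is recorded. If one arm has the longer look-back, equal recorded history means less true history in that arm, because more true cases sit among the other arm's patients coded negative. The plan's balance check uses the same recorded variables and would pass. Sections 8.9.1.1 to 8.9.1.4, on misclassification, information bias, selection and confounding, do not mention unequal look-back.

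**Working it through.** The protocol states no figure on this point, so there is nothing to reproduce. The check asks whether the mechanism operates and how large it could be.

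**Inputs from the protocol.** Section 8.5 expects 3,850 romosozumab and 8,500 PTH-analog patients, so the romosozumab share is s = 3,850/12,350 = 0.31.

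**Assumptions (none is in the protocol).** True prevalence p is equal in both arms. Remote events are spread evenly over years 1 to 15 before index. Look-back L is 1, 3, 6 or 10 years, with shares 10/20/30/40% in a long-look-back arm and 40/30/20/10% in a short one. The outcome rate ratio (RR) for the history is 2.5.

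**Step 1: capture.** The visible share at look-back L is (L − 1)/14, which is 0, 0.143, 0.357 and 0.643.
- Long arm: c = 0.2×0.143 + 0.3×0.357 + 0.4×0.643 = 0.393.
- Short arm: c = 0.3×0.143 + 0.2×0.357 + 0.1×0.643 = 0.179.

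**Step 2: weighting on recorded history alone.** Recorded prevalence is p·c, and weighting sets both arms to the pooled value t. Weighted true prevalence in an arm is t + (1 − t)·p(1 − c)/(1 − p·c). The bias factor on the HR is approximately [1 + (RR − 1)·true prevalence in romosozumab] / [1 + (RR − 1)·true prevalence in comparator].

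**Step 3: remote MI at p = 5%, romosozumab long.**
- Recorded prevalence is 1.96% vs 0.89%, so t = 0.31×0.0196 + 0.69×0.0089 = 0.0123.
- Romosozumab: 0.0123 + 0.9877×0.0304/0.9804 = 4.28%.
- PTH analogs: 0.0123 + 0.9877×0.0411/0.9911 = 5.32%.
- SMD on true history is −0.048. Bias factor is (1 + 1.5×0.0428)/(1 + 1.5×0.0532) = 0.986.

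**Step 4: the other cases by the same formulas.**

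| True prevalence, both arms | Longer look-back | Weighted true prevalence, romosozumab vs PTH | SMD | HR bias factor |
|---|---|---|---|---|
| 5% | romosozumab | 4.3% vs 5.3% | −0.048 | 0.986 |
| 5% | PTH analogs | 5.7% vs 4.7% | 0.046 | 1.014 |
| 10% | romosozumab | 8.6% vs 10.6% | −0.068 | 0.974 |
| 10% | PTH analogs | 11.4% vs 9.4% | 0.065 | 1.026 |
| 40% (fracture-type) | PTH analogs | 43.8% vs 38.1% | 0.116 | not given (RR 2.5 was chosen for MI) |
| 5% or 10% | equal | unchanged | 0.000 | 1.000 |

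In every row the recorded covariate is perfectly balanced after weighting. The fracture-type case exceeds the plan's own 0.1 limit on the true variable while the reported SMD would be zero.

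**Step 5: effect of the fix.** Weighting on recorded history within each look-back category returns 5.00% vs 5.00% in the 5% case (SMD 0.000, factor 1.000). If true history itself differs, at 3% vs 5%, an SMD of about −0.07 to −0.08 remains after the fix, because events beyond anyone's look-back are still unseen.

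**The case against.** **Left to the SAP.** Section 8.9.3 defers model-building decisions to the SAP, which could add look-back length. That is fair, but the protocol itself fixes the covariate list and windows, and the reduction it describes there is dropping low-prevalence covariates. The open window is a choice made in this document.

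**Already covered by other checks.** Section 8.9.1.1 plans a comparison with a closed database, Section 8.9.4 a test of differential missingness, and negative controls and quantitative bias analysis are planned as well. These may signal a problem, but none corrects unequal look-back in the weights.

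**Record length might predict treatment only.** Section 8.7.2.4 advises against covariates tied to exposure but weakly to outcome. That caution is reasonable, and it is why look-back should first be described by cohort. Here, however, record length determines how well a confounder is measured.

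**The sign is not known.** A reader might infer that romosozumab patients have the longer look-back, so that the HR is pushed below 1 and harm is masked. The support would be Section 8.9.1.1: "Since romosozumab appears to have more complete data related to other specific therapies in the MID-NET system". That sentence concerns care outside an open network, not years of record per cohort. It makes unequal capture plausible, but it does not fix the direction for look-back. This objection stands in full.

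**The size is modest.** A reader might also expect a bias of 5% or more for remote MI. At 10% prevalence, RR 3 and capture of 80% vs 50% against 60,000 alendronate patients, the formula gives 0.951 (1.048 with the captures swapped). With events spread evenly over years 1 to 10, visible share (L − 1)/9, those captures need mean look-backs of about 8.2 and 5.5 years, and the protocol supports no such gap. The model also holds one-year cardiovascular comorbidities and drugs, so the conditional RR of an old MI is probably smaller.

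**Conclusion.** The point holds as a conditional one. The protocol reads fracture history, prior anti-osteoporosis drugs and remote MI and second-event history over windows that vary by patient, from 365 days upward, and omits look-back length from the covariates that form the propensity model. If look-back differs between arms within index year, true history can be unbalanced in either direction behind satisfactory SMDs.

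Under the stated assumptions the shift is about 1 to 3% on the HR for remote MI, with a larger imbalance for a common history such as fracture. It is zero if look-back is equal. For scale, the narrowest interval in Table 4 is 0.70 to 1.45, so remote MI alone would not overturn a conclusion. But this is bias rather than noise, and several covariates share it. The documents do not support a claim that harm is masked, or that all prior-MI adjustment is affected.

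One condition comes first. If the 365-day span in Section 8.2.1 governs, look-back is uniform, the remote-event rows are empty, and the defect becomes a contradiction with Sections 8.2.4 and 8.3.3.

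**What to change.** 1. Report look-back length (first MID-NET record to index date) by cohort, with its SMD.
2. Add it in categories to Table 3 and to the propensity model. The calculation above weighted on recorded history within look-back category, so the SAP should consider the interaction with the remote-event rows.
3. Add one sensitivity analysis that reads all history covariates over a common fixed look-back, in patients who have that much record.
4. Reconcile the 365-day data span in Section 8.2.1 with the use of all historical data in Sections 8.2.4 and 8.3.3.
5. Reconcile the Section 8.3.3 text with Table 3 on the window for cardiovascular risk factors and cardioprotective therapies.

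The cost is one variable derived from data already extracted, one extra run and a text correction. Weights may become slightly more variable, and the sensitivity run will have fewer patients and less precision. The change does not recover care given outside MID-NET, nor correct under-recording where true history differs between arms. Appendix C schedules completion of the SAP for December 2025 and the start of analysis for January 2026, so this should be settled before then.
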